## 2.3 Study Endpoints

### 2.3.1 Primary Efficacy Endpoint

The primary efficacy endpoint is the change from baseline in urine protein:creatinine ratio (UPCR) at Week 12.

### 2.3.2 Secondary Efficacy Endpoints

Secondary efficacy endpoints include:

- Change from baseline in eGFR calculated by the Chronic Kidney Disease Epidemiology Collaboration (CKD-EPI) cystatin C equation, CKD-EPI Creatinine equation, CKD-EPI Creatinine-Cystatin C equation and modification of diet in renal disease (MDRD) Creatinine equation at Weeks 12 and 24
- Proportion of subjects achieving complete renal remission by the following definition at Weeks 12 and 24:
  - reduction in UPCR to <0.3 g/g and
  - serum albumin within normal range and
    - for patients with abnormal serum creatinine levels at baseline, return to normal levels for that age group
    - or
    - for patients with normal serum creatinine levels at baseline, final value within 20% of baseline levels
- Proportion of subjects achieving partial remission by the following two definitions assessed at Weeks 12 and 24:
  - UPCR reduction of  $\geq 50\%$  from baseline and UPCR  $< 3.5 \text{ g/g}$
  - decrease in UPCR to less than 1.5 g/g and at least a 40% reduction in proteinuria from baseline

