| Section(s) | Original Text | Revised Text | Rationale for Change |
|--|---|--|---|
| SYNOPSIS, Efficacy Assessments & Bullet 2 | 
 Proportion of subjects achieving complete renal remission (UPCR 0.3 g/g; eGFR normal or not less than 20% below baseline)... assessed at Weeks 12 and 24. | 
 Proportion of subjects achieving complete renal remission at Weeks 12 and 24 
Complete Remission (includes all of the following):
 
 - reduction in UPCR to <0.3 g/g - Serum albumin within normal range - For subjects with abnormal serum creatinine levels at baseline, return to normal levels for that age group - For subjects with normal serum creatinine levels at baseline, final value within 20% of baseline levels | Clarified the definition of complete renal remission |
| None | 
... or partial remission (UPCR decreased by 50% from baseline; UPCR <3.5g/g; and eGFR normal or not less than 20% below baseline), assessed at Weeks 12 and 24.
 | 
 Proportion of subjects achieving partial remission at Weeks 12 and 24 by the following two different definitions: 
 - UPCR reduction of ≥50% from baseline and UPCR <3.5 g/g - decrease in UPCR to less than 1.5 g/g and at least a 40% reduction in proteinuria from baseline assessed | Clarified the definition of partial remission and added a second method for calculating partial remission |
| SYNOPSIS, Health Related Quality of Life Assessment | Change from baseline in domains assessed by Short Form 36 version 2 (SF-36 v2 and EQ-5D-5L) through Week 12 and Week 24 | Change from baseline in domains assessed by answers to the SF-36 v2 and EQ-5D-5L questionnaires through Week 12 and Week 24 | To clarify the instruments used |
| SYNOPSIS & Section 8.4 Exploratory Pharmacodynamic Assessments, bullet 5 | 
 Change from baseline in... biomarkers...may include measurement of all or of a subset of the following: | 
 Change from baseline in... biomarkers...may include measurement of: | To harmonize the Synopsis with Section 8.4 (error) |

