The relationship between PK and serum albumin and between PK and UPCR will be explored where possible.

Efficacy Assessments

Efficacy will be evaluated by assessment of urine protein:creatinine ratio (UPCR), urine albumin:creatinine ratio (UACR) and estimated glomerular filtration rate (eGFR)

The primary efficacy endpoint is:

- Change from baseline in urine protein:creatinine ratio (UPCR)

Secondary endpoints include:

- Change from baseline in eGFR calculated by the CKD-EPI cystatin C equation, CKD-EPI Creatinine equation, CKD-EPI Creatinine-Cystatin C equation and MDRD Creatinine equation at Weeks 12 and 24
- Proportion of subjects achieving complete renal remission **at Weeks 12 and 24**

Complete Remission (includes all of the following):

- **Reduction in UPCR to < 0.3 g/g**
- **Serum albumin within normal range**
- **For subjects with abnormal serum creatinine levels at baseline, return to normal levels for that age group**

- For subjects with normal serum creatinine levels at baseline, final value within 20% of baseline levels
- Proportion of subjects achieving partial remission at Weeks 12 and 24 by the following two different definitions:
 - UPCR reduction of $\geq 50\%$ from baseline and UPCR <3.5 g/g
 - decrease in UPCR to less than 1.5 g/g and at least a 40% reduction in proteinuria from baseline

Health Related Quality of Life Assessment

Change from baseline in domains assessed by **answers to the SF-36 v2 and EQ-5D-5L questionnaires** through Week 12 and Week 24

Exploratory Pharmacodynamic Assessments

Blood (plasma and serum) and urine samples will be collected according to the [Time and Events Table](#) for PD biomarker measurements.

Exploratory assessments may include:

- Profile of FSGS related gene mutations;
- Change from baseline in urinary MCP-1:creatinine ratio;
- Change from baseline in urinary albumin to creatinine ratio (UACR)
- Change from baseline in blood monocytes, T, B and NK cells
- Change from baseline in other urinary and blood exploratory biomarkers potentially associated with activity of FSGS or inhibition of the CCR2/MCP-1 pathways. These may include measurement of:

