9.2.2. Secondary Efficacy Endpoints

- Change from baseline in eGFR calculated by the CKDEPI cystatin C equation, **CKD-EPI Creatinine equation, CKD-EPI Creatinine-Cystatin C equation and MDRD Creatinine equation** at Weeks 12 and 24
- **Proportion of subjects achieving complete renal remission at Weeks 12 and 24**
Complete Remission (includes all of the following)
 - **reduction in UPCR to < 0.3 g/g**
 - **Serum albumin within normal range**
 - **For patients with abnormal serum creatinine levels at baseline, return to normal levels for that age group**
 - **For patients with normal serum creatinine levels at baseline, final value within 20% of baseline levels**
- Proportion of subjects achieving partial remission **by the following two different definitions assessed at Weeks 12 and 24:**
 - **UPCR reduction of $\geq 50\%$ from baseline and UPCR < 3.5 g/g**
 - **decrease in UPCR to less than 1.5 g/g and at least a 40% reduction in proteinuria from baseline**

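### The 20% creatinine band in the complete-remission definition has no stated direction, so as written a fall in creatinine of more than 20% fails it

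*SAP*

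**What the plan says.** Protocol Section 9.2.2 introduces the endpoint with "Complete Remission (includes all of the following", and the SAP joins the conditions with the word and, beginning with "reduction in UPCR to <0.3 g/g and". Normal serum albumin is the second condition. The third depends on baseline creatinine:

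- Abnormal baseline (SAP 2.3.2): "for patients with abnormal serum creatinine levels at baseline, return to normal levels for that age group".
- Normal baseline (SAP 2.3.2): "for patients with normal serum creatinine levels at baseline, final value within 20% of baseline levels".
- Normal baseline (Protocol 9.2.2): "For patients with normal serum creatinine levels at baseline, final value within 20% of baseline levels".
- Normal baseline (Protocol Synopsis): "For subjects with normal serum creatinine levels at baseline, final value within 20% of baseline levels".

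SAP Section 3.4.2 analyses the remission proportions at Weeks 12 and 24 and refers back to Section 2.3.2 for the definition. No current section limits the 20% band, "final value within 20% of baseline levels", to a rise in creatinine.

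**The concern.** A renal-function condition in a remission definition is normally there to exclude subjects whose function has worsened while their proteinuria improved. A band with no direction also excludes subjects whose creatinine has fallen.

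Two features of the documents suggest that this was not intended. First, the abnormal-baseline condition requires a return to normal and sets no limit on the size of the fall. A 40% fall can therefore qualify one subject while a 22% fall disqualifies another, depending on which side of the normal limit each began. Second, where the protocol describes deteriorating renal function (Synopsis and Section 4) or lists creatinine in the single-subject guidelines (Table 2, Section 4.2.1), only an increase counts. Those sections are cited for direction only.

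As context, the summary of changes for Amendment 4.0 shows that the superseded wording was one-sided and based on eGFR: "eGFR normal or not less than 20% below baseline". That difference is not itself an error, but the log describes the change as a clarification and records no decision to exclude improvement.

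What is at stake is the complete-remission proportion in arms of 10, where a single subject is visible in the result.

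**Working it through.** The documents give no rate, power or sample size that depends on this definition, so there is no figure of the plan's to reproduce.

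**1. The rule as written against a one-sided rule.** Let r = final creatinine / baseline creatinine.

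- As written: pass if |r − 1| ≤ 0.20, that is 0.80 ≤ r ≤ 1.20.
- One-sided: pass if r ≤ 1.20.

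| r | As written | One-sided |
|---|---|---|
| below 0.80 | fail | pass |
| 0.80 to 1.20 | pass | pass |
| above 1.20 | fail | fail |

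The rules differ only below r = 0.80. With illustrative values, 1.10 to 0.86 mg/dL is 0.86/1.10 − 1 = −21.8% and fails as written; 1.10 to 0.88 is −20.0% and passes. Both pass the one-sided rule.

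**2. What r = 0.80 means for function.** If function is proportional to 1/creatinine, the lower edge is 1/0.80 − 1 = 25% improvement. An 18% fall in creatinine (r = 0.82, a gain of 22%) still passes. If eGFR instead varies as creatinine to a power between −0.4 and −1.2 (assumed range), the edge lies at 0.80^−0.4 − 1 = 9% to 0.80^−1.2 − 1 = 31%.

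**3. How often r falls below 0.80.** The documents give no SD for creatinine change. Assume that log r is normal with mean 0 and SD 0.10 to 0.15:

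- SD 0.10: Φ(ln 0.80 / 0.10) = Φ(−2.23) = 0.013.
- SD 0.15: Φ(ln 0.80 / 0.15) = Φ(−1.49) = 0.068.

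So 1.3% to 6.8% of subjects with normal baseline creatinine who meet the other two conditions would be excluded. If each of the four arms had one or two such subjects (also an assumption), the trial would have 4 to 8. The expected number affected is then 4 × 0.013 = 0.05 to 8 × 0.068 = 0.54.

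**4. Effect of one subject.** With 10 per arm (SAP 2.2.1), one subject is 1/10 = 10 percentage points. The 90% Clopper-Pearson interval named in SAP 3.4.2 is 0 to 25.9% for 0/10 and 0.5% to 39.4% for 1/10.

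**5. Where else such a subject is counted.** Entry requires UPCR of at least 1 g/g at screening (Protocol 5.2). If baseline is also at least 1 g/g, a final value below 0.3 g/g is a reduction of more than 1 − 0.3/1 = 70%. That meets both partial-remission definitions (at least 50% with UPCR below 3.5 g/g; below 1.5 g/g with at least 40%). Even a baseline of 0.6 g/g gives a reduction of more than 1 − 0.3/0.6 = 50%. Neither definition has a creatinine condition or excludes complete remitters.

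**The case against.** The strongest case against the point is that it changes almost nothing. The subject is lost only from the complete-remission row. Partial remission, and normally the 30% UPCR responder analysis, still count the subject; duration of response (SAP 3.4.2) accepts either kind of remission; and four eGFR equations capture any gain in function. The frequency rests on an SD that the documents do not give. Complete remission is one of several unranked secondary endpoints in an exploratory study with no multiplicity adjustment (SAP 3.1.5). All of that stands, and it sets the size of the point.

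It can also be said that nobody knows how the rule will be coded, because the detailed programming specifications are a separate document (SAP Section 7). That is true, but it does not settle the matter. If a programmer assumes a one-sided intent, the endpoint is decided by a choice that the SAP does not record.

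A reader might go further and infer that the rule is biased against an effective dose. The documents do not support that. The 1.3% to 6.8% is calculated with no mean change, so it describes random variation that would affect otherwise remitting subjects in every arm at the same rate. The documents give no figure for a treatment-related fall in creatinine, and nothing in them predicts falls above 20% from a normal baseline. Nor do the two creatinine conditions work in opposite directions: neither rewards a rise. They differ only in that one limits a fall and the other does not.

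Finally, Amendment 4.0 introduced the present wording deliberately, and its source is not visible. A symmetric band could be intended, but no reason for one is given.

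**Conclusion.** The point holds as a minor flaw in an endpoint definition. For subjects with normal baseline creatinine, the stated rule classifies a creatinine fall of more than 20% in the same way as a rise of more than 20%, and no other current text corrects it. The consequence is confined to the complete-remission proportion at Weeks 12 and 24. The expected number affected is below one, given the assumed SD, no mean change and the assumed count of remitters; if one subject were affected, that arm's proportion would change by 10 percentage points. The primary endpoint, both partial-remission definitions and the sample size are untouched. No claim of bias against any dose follows.

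**What to change.** Before unblinding, reword the normal-baseline creatinine condition in SAP 2.3.2 to *final value not more than 20% above baseline*, and record the change in SAP Section 6. If the sponsor does intend a symmetric band, the SAP should say so and give the reason.

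The SAP supersedes the protocol's statistical methods (Protocol Section 9, SAP Section 1), so Protocol 9.2.2 and the Synopsis can be aligned at the next amendment. Protocol Section 9 also asks for an amendment when principal features change, so the sponsor should confirm that this definition is not regarded as one.

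The cost is one phrase in a revised SAP and one condition in the programming. No data collection, sample size or treatment rule changes.

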### 2.3.3 Exploratory Endpoints

Exploratory endpoints include:

- Change from baseline of proteinuria in subjects treated with CCX140-B versus placebo over time
- Change from baseline (absolute and percent change) in urinary albumin:creatinine ratio (UACR). The response rate across dose groups for patients achieving 30% reduction in

UACR from baseline at Week 12 will be calculated, with the number of subjects in the respective treatment group in the ITT (or PP) population being the denominator. The analysis will be repeated for reductions of 20%, 40% and 50%.

- Change from baseline in urinary MCP-1:creatinine ratio
- Change from baseline in blood monocytes (absolute and %), T, B and NK cells
- Change from baseline in Health-related Quality of Life changes based on Short Form 36 version 2 (SF-36 v2) and EuroQuality of Life-5 Domains-5 Levels (EQ-5D-5L) questionnaires
- Change from baseline in serum albumin
- Relationship among PK, eGFR, serum albumin and UPCR

#### 2.3.4 *Pharmacokinetic Endpoints*

Concentrations of CCX140 will be determined in plasma from 4.0-mL blood samples collected in K2EDTA tubes according to Table 1. The following parameters will be determined, where possible:

- Cmax Maximum plasma concentration
- Tmax Time of maximum plasma concentration
- AUC0-6 Area under the plasma concentration-time curve from Time 0 to Hour 6 on Day 1 and Day 15
- Cmin Trough level plasma concentrations at post-Day 1 visits

On Days 1 and 15, samples will be taken at pre-dose, 0.5, 1, 2, 3, 4, and 6 hours after dosing. The blood samples collected on the other relevant study days need to be collected prior to taking the CCX140-B/ placebo dose.

The relationship between PK and serum albumin and between PK and UPCR may be explored, where possible.

Total plasma concentrations of CCX140 will be determined using validated analytical methods. These plasma samples may also be used to measure other markers associated with FSGS.

#### 2.3.5 *Pharmacodynamic Endpoints*

Blood samples (plasma and serum) and urine samples for PD measurement will be collected according to the schedule in Table 1.

In addition to those included in the exploratory efficacy endpoints, the following PD endpoints may be assessed if measured:

- Profile of FSGS related gene mutations;
- Change from baseline in other urinary and blood exploratory markers potentially associated with activity of FSGS or inhibition of the CCR2/MCP-1 pathways. These may include measurement of:

- o Transforming growth factor-beta (TGF-B), connective tissue growth factor (CTGF), N-acetylglucosamine (NAG),  $\beta$ 2 microglobulin, adiponectin, C-reactive protein (CRP), cystatin C, synaptopodin, neutrophil gelatinase-associated lipocalin (NGAL), liverfatty acid-binding protein (LFABP), kidney injury molecule-1(KIM-1), intact PTH, leptin, reistin, chemerin, retinol binding protein 4 (RBP-4), MCP-1, IL-1 $\beta$ , IL-6, suPAR, miR-193a, CLCF-1 and TNF- $\alpha$ .

### 2.3.6 Safety Endpoints

#### 2.3.6.1 Adverse Events

Safety endpoints related to adverse events include subject incidence of treatment-emergent adverse events (TEAE), adverse events leading to study withdrawal, and serious adverse events. An adverse event will be considered treatment-emergent if the start date of the event is on or after the date of administration of the first dose of study medication.

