- **The subject will be given instructions and supplies for the urine collections on the day before the next visit (kit for first morning void and jug for 24-hour urine collection)**
 - **Collect the first morning void the day before the first visit (Day 0) and put in the smaller container.**
 - **Collect all urine for 24 hours starting AFTER the first morning void, including first morning void on the day of the Study Day 1 visit, in the big jug.**
 - **Keep specimens refrigerated until they are brought to the site at the Study Day 1 visit.**

7.2. Study Day 1

If eligible for the study, the subject will visit the study center on Day 1. The following procedures will be performed before taking the first dose of CCX140-B:

- A complete physical examination
- Vital signs (weight, temperature, blood pressure, heart rate after at least 3 minutes of rest)

- A 12-lead ECG, after at least 3 minutes of rest, will be recorded and assessed for any clinically significant abnormality
- Blood samples will be collected for serum chemistry (including coagulation panel and lipids), pregnancy test (in women of childbearing potential), hematology, DNA, plasma MCP-1, PK, PD (including lymphocyte subsets) and baseline measurements
- **Process the first morning void urine sample collection for quantitative urinalysis, UPCR, UACR, Cystatin C, Urine MCP-1, MCP-1/creatinine ratio and urine PD assessment**
- **Process the 24-hour urine sample collection for quantitative urinalysis, UPCR, UACR, Cystatin C, Urine MCP-1, MCP-1/creatinine ratio urine PD assessment and urine protein excretion/day**
- Any pre-treatment adverse events (from time of the screening visit) will be recorded
- Subjects will be asked to complete the SF-36 v2 and EQ-5D-5L
- Subjects will be asked to complete their diary each day immediately after each dose
- The ACTG Brief Peripheral Neuropathy Screening Tool will be administered

Once deemed eligible, the following procedures will be performed:

- Study medication (in kits, containing 4-week supply bottles of CCX140-B/Placebo), will be provided to the subject with dosing instructions
- The subject will be asked to take the first dose of CCX140-B while at the study center and should remain at the study center for observation at the PI's discretion
- The time of the dosing of CCX140-B will be recorded

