8.2.3. Adverse Events

An adverse event (AE) is defined as any untoward medical occurrence associated with the use of a drug in humans, whether or not considered drug related. An adverse event could therefore be any unfavorable and/or unintended sign (including abnormal laboratory findings), symptom, or disease temporally associated with the use of the drug, whether or not considered related to the drug. This definition includes intercurrent illnesses or injuries, and exacerbation of pre-existing conditions.

An unexpected adverse event is an adverse event that is not identified in nature, severity, or frequency in the current Investigator's Brochure, or that is of greater severity than expected based on the information in the Reference Safety Information listing within the Investigator's Brochure.

All adverse events occurring in subjects who have been randomized to treatment will be recorded in the EDC system and will be reported in accordance with regulatory requirements. Adverse events reported prior to commencement of administration of study medication will be considered pre-treatment events. If subject stops taking CCX140-B/placebo, adverse event reporting should be continued as long as study is active.

All adverse events will be monitored until resolution or, if the adverse event is determined to be chronic, until a cause is identified. If an adverse event remains unresolved at the conclusion of the study, a clinical assessment will be made by the Investigator and the Sponsor's Medical Monitor to determine whether continued follow-up of the adverse event is warranted.

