### 3.6.1 Adverse Events (AEs)

An overview of AEs will be provided including counts and percentages of subjects (and event counts) with the following:

- Any TEAEs (overall and by maximum severity)
- Any study drug related TEAEs (overall and by maximum severity)
- Any treatment-emergent serious AEs (TESEAEs)
- Any TEAEs leading to discontinuation of study drug
- Any AEs leading to death

Counts and percentages of subjects (and event counts) will also be presented by system organ class (SOC) and preferred term (PT) using the Medical Dictionary for Regulatory Activities (MedDRA) Version 20.1 any TEAEs and TESEAEs for 3 Safety Populations separately. Counts and percentages of subjects (and event counts) will also be presented by PT in decreasing frequency for any TEAEs and TESEAEs for 3 Safety Populations (see 3.2.4 for definitions) separately.

TEAEs for the Safety Population in each period are defined as an event with a start date on or after the first study drug treatment in each period and up to the final observation in each period. Treatment periods for analysis of adverse event are defined in Section 3.2.4. TEAEs for the All CCX140-B Treated Population are defined as an event with a start date on or after the first dose of CCX140-B up to the final observation.

Listings will be presented specifically for SAEs and TEAEs leading to discontinuation of study drug.

The severity of AEs was assessed by the investigator using the following protocol definitions:

- Mild (Grade 1): no limitation of usual activities
- Moderate (Grade 2): some limitation of usual activities
- Severe (Grade 3): inability to carry out usual activities
- Life-threatening (Grade 4): an immediate risk of death
- Death (Grade 5)

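### TEAEs are defined by start date only, so a worsening kept on its original AE record drops out of some or all of the TEAE tables

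*SAP*

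**What the plan says.** The SAP has three TEAE rules, and all of them test the start date.

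- Overall (SAP 2.3.6.1): an event is "considered treatment-emergent if the start date of the event is on or after the date of administration of the first dose" of study medication.
- By period (SAP 3.6.1), for Safety_A and Safety_B: "an event with a start date on or after the first study drug treatment in each period".
- All CCX140-B Treated (SAP 3.6.1): "an event with a start date on or after the first dose of CCX140-B up to the final observation".

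The tables by system organ class and preferred term are built on these flags, separately for the three safety populations of SAP 3.2.4. The overview row "Any TEAEs leading to discontinuation of study drug" uses the same flag, and so does its listing: "Listings will be presented specifically for SAEs and TEAEs leading to discontinuation of study drug". The deaths row, "Any AEs leading to death", is not limited to TEAEs.

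The protocol uses the term TEAE without defining it. On Study Day 1 (Protocol 7.2), "Any pre-treatment adverse events (from time of the screening visit) will be recorded". Protocol 8.2.3 adds: "Adverse events reported prior to commencement of administration of study medication will be considered pre-treatment events". The same section counts an exacerbation of a pre-existing condition as an adverse event. It does not say whether a recorded event that rises in grade gets a new record with its own start date.

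**The concern.** A TEAE definition usually captures events that begin or get worse on treatment. This one captures only the first kind. Whether a worsening is counted therefore depends on how a site records it, and with about 40 sites planned and no written rule, the same clinical course could count at one site and not at another.

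Safety and tolerability is a primary objective. Week 12 also changes exposure: at the planned open-label dose of 15 mg twice daily, the total daily dose goes from 0 to 30 mg for placebo subjects, from 5 to 30 mg for the 5 mg once-daily group, and from 20 to 30 mg for the 10 mg twice-daily group. Safety_B is the analysis that should show what follows, and a worsening of an ongoing event is what the rule can leave out.

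Among the special-interest topics in Protocol 4, infection depends most on AE reporting. Outside it there is only nonspecific cover: white-cell differential, urinalysis and body temperature. A mild infection can be ongoing at the switch, because Protocol 5.4 bars entry to the extension only where the investigator judges that a new infection rules out added immunosuppression.

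**Working it through.** The plan gives no figure on this point. The check applies the three rules to each pattern of onset and worsening, then sizes one missed subject.

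**Inputs**
- Period A runs from Day 1 to Week 12, and Period B from Week 12 to end of study (SAP 3.2.4).
- First CCX140-B dose: Day 1 in the active arms; the first open-label dose at Week 12 for placebo subjects who continue (SAP 2.2.2).
- 10 subjects per arm, 40 in total (SAP 2.2.1).
- Assumption: the worsening stays on the original AE record, so the start date does not change.

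**Step 1. Rules as written**

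| Arm | Onset | Worsens in | Safety_A | Safety_B | All CCX140-B Treated |
|---|---|---|---|---|---|
| Placebo | Screening | A or B | no | no | no |
| Active | Screening | A or B | no | no | no |
| Placebo | Period A | B | yes | no | no |
| Active | Period A | B | yes | no | yes |

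A screening-onset event also fails the overall rule in SAP 2.3.6.1. It is therefore not a TEAE leading to discontinuation either, in the count or in the listing.

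**Step 2. With a clause for increased severity added**

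| Arm | Onset | Worsens in | Population that gains the event |
|---|---|---|---|
| Placebo | Screening | A | Safety_A |
| Active | Screening | A | Safety_A, All CCX140-B Treated |
| Any | Screening | B | Safety_B, All CCX140-B Treated |
| Placebo | Period A | B | Safety_B, All CCX140-B Treated |
| Active | Period A | B | Safety_B |

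**Step 3. Size of one missed subject**, who has no other event of that term in the population concerned: 100 × 1/n percentage points.
- One arm, n = 10: 100/10 = 10 points.
- Safety_B pooled over arms, all 40 continuing: 100/40 = 2.5 points.
- All CCX140-B Treated, n = 30 + k, where k is the number of placebo subjects who enter the extension: k = 10 gives 2.5; k = 8 gives 100/38 = 2.63; k = 1 gives 100/31 = 3.23; k = 0 gives 100/30 = 3.33. The last value can arise only for an active-arm subject with screening onset.

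Which denominator applies in Safety_B is not fully settled. SAP 3.2.4 tabulates safety data by randomized group, with actual treatment used if the wrong drug was taken. SAP 3.6 says actual treatment throughout.

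**The case against.** The strongest reply is that Protocol 8.2.3 already solves this. It treats an exacerbation of a pre-existing condition as an adverse event and requires all adverse events in randomized subjects to be recorded. On that reading a worsening is a new event with its own start date, and it counts under every rule. The reading is reasonable, and where sites follow it nothing is missed. But the section gives no instruction to split records. It classes events reported before dosing as pre-treatment, and nothing reclassifies them later.

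The second reply is that the information survives elsewhere. Much of it does:
- the SAE listing and the deaths row (SAP 3.6.1);
- laboratory shift tables (3.6.2) and the neuropathy screening summaries (3.6.6);
- full subject listings (SAP 7), which can be read case by case in a trial of 40;
- withdrawal reasons by treatment group (3.3.1), and adverse events leading to study withdrawal, which SAP 2.3.6.1 names as an endpoint without a TEAE limit (Protocol 9.3.6 does say TEAE);
- DMC review of unblinded safety data (SAP 4).

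This limits the gap mainly to incidence tables for non-serious clinical events. A listing does not replace an incidence comparison.

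Third, for active-arm subjects a Period A event that worsens in Period B is still counted in Safety_A and in All CCX140-B Treated. Assigning it to the period of onset is a convention. That stands: in the active arms this is a period-attribution gap, not a lost event.

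A reader might also infer that a mild screening event which becomes moderate and drug-related, and so ends treatment under Table 2 of Protocol 4.2.1, would go uncounted. The documents do not carry that. The Table 2 row halts treatment, reassesses after two weeks and refers to the Medical Monitor; permanent discontinuation is a further step. The example also needs a drug-related rating on a record that predates dosing, and an investigator who judges the worsening drug-related may well enter it as its own event.

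**Conclusion.** The point holds in conditional form. As written, the rules leave out a worsening that stays on its original record: from every TEAE table if onset was in screening, and from Safety_B if onset was in Period A. The clearest misattribution concerns placebo subjects whose Period A event worsens on their first CCX140-B exposure. That event is missing from All CCX140-B Treated and is credited only to placebo in Safety_A, where the placebo incidence does not change.

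One missed subject is worth about 10 points in an arm of 10, or about 2.5 to 3.3 points in All CCX140-B Treated. These are sizes per subject, not expected effects. The frequency is unknown, and it is zero if sites open new records or if no recorded event worsens.

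Two stronger conclusions are tempting but unsupported. One is that the comparison is biased in favour of CCX140-B: the screening-onset omission applies to every arm, and nothing in the documents says where it would fall more often. The other is that a later, higher grade would be shown under placebo in Safety_A: the documents do not say how grade over time is stored. The point is a cheap improvement to a primary safety analysis and does not show that the safety tables will be wrong.

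**What to change.** In SAP 2.3.6.1 and 3.6.1, define a TEAE as an event that starts, or increases in severity, on or after the relevant first dose: of study drug for the overall rule, of the period for Safety_A and Safety_B, and of CCX140-B for All CCX140-B Treated. Apply the same definition to TEAEs leading to discontinuation. Before unblinding, review AE records ongoing at first dose and at Week 12 and query the date of any worsening. Where it cannot be dated, flag the event in the listing.

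The cost is wording in two sections, a small review before database lock in about 40 subjects, and some site queries. SAP version 1.0 already describes DMC meetings in the past tense, so some of the dating would be retrospective. If the review finds no worsening, the tables stay as they are.
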